1.6. Primary Sample Size Calculations

The hardships of the COVID pandemic and its subsequent impact on in-person patient care resulted in our revision of our initial sample size approach. Specifically: 1) based on recent guidelines^{28, 29}, we will not adjust our two primary hypotheses for multiplicity as they do not involve different endpoints (i.e., both hypotheses test EPDS scores). Past references^{28, 29} have indicated when multiple hypotheses test the similar underlying outcomes, no adjustment for multiplicity is required. Unlike superiority analyses which determine success based on p-values, non-inferiority analyses determine success based on the pre-specified non-inferiority margin and the confidence interval around the difference (outlined in [3.4.1](#)); and 2) The non-inferiority margin for in-person compared to telemedicine has been changed to 13% ([1.6.2.1](#)).

1.6.1. Primary Aim 1 (Specialist vs. Non-Specialist) Comparison

The primary outcome measure is an EPDS mean score at 3 months post-randomization. The sample size calculation is based on an EPDS mean estimate of 7.93 (SD=4.68)³⁰. Using a non-inferiority margin of 10% (i.e., EPDS score of 0.79 in relation to the mean), and an alpha=0.05, we require 431 participants in each of the two groups (SP, NSP) to provide greater than 80% power ([Table 3](#)). To account for 10% drop out, the sample size is inflated to **N=958** (479 per group, SP vs. NSP). All sample size calculations were run using PASS Version 12³¹.

Table 3: Power Analysis of a Non-Inferiority Test of the Difference of Two Means

Power	N1/N2	Non-Inferiority Margin (NIM)	Actual Difference	Significance Level (Alpha)	Beta	Standard Deviation 1 (SD1)	Standard Deviation 2 (SD2)
0.80022	431/431	0.793	0.000	0.05000	0.19978	4.680	4.680

1.6.2. Primary Aim 2 (Telemedicine vs. In-Person) Comparison

The primary outcome measure is an EPDS mean score at 3 months post-randomization. The sample size calculation is based on an EPDS mean estimate of 7.93 (SD=4.68)³⁰. Using a non-inferiority margin of 13% (i.e., EPDS score of 1.03 in relation to the mean), and an alpha=0.05, we require an additional 268 IP participants ([Table 4](#)).

Table 4: Non-inferiority margin in relation to sample size for Phase 3 comparisons

Non-inferiority margin	Power	Sample size per primary question	Total sample size + 10% dropout*	Total sample size + 20% dropout
10%	80%	431	958	1078
13%	80%	241	536 (268 per group)	604
14%	80%	221	492 (246 per group)	556

*Current dropout rates are <10% at primary outcome of 3-months post-randomization

When combined with the 958 TM participants, this yields a total study sample size of N=1,226 which accounts for 10% loss to follow-up ([Table 5](#)).

Table 5: Primary aims and required sample sizes

Primary Aim [¥]	Non-inferiority Margin	Power	Required sample size + 10% drop out
SP vs. NSP [¥]	10%	88%	958 telemedicine
IP vs. Telemedicine	13%	80%	268 in-person*
	Total		N=1226*

[¥]We acknowledge that the in-person sample is contained in the first hypothesis. This will result in the SP vs NSP comparison having up to 88% power. *We will over-recruit to account for protocol deviations where participants were switched from in-person to telemedicine due to the COVID-19 pandemic.

1.6.2.1 Justification of Revised Non-inferiority Margin

Pandemic-related disruptions have resulted in difficulties with recruitment to the IP arms. To account for this, the non-inferiority margin for the TM vs. IP comparison was increased from 10% to 13%, thereby reducing the required IP sample size. This increase is justified by the literature. We only identified one non-inferiority trial that used the EPDS and a non-inferiority margin of 15%³². We did find that a non-inferiority psychotherapy trial using a PHQ-9 of 1.9³³, which is comparable to the EPDS³⁴, with similar sensitivity among numerous perinatal populations. The justification of a clinically meaningful non-inferiority margin is based on the following approach by Richards' et al COBRA Trial (2017)³³:

1. Start off with a comparison of superiority of the one treatment to control in the past literature. They looked at a meta-analysis of their treatment of interest versus control.
2. Take half of this effect size, as they indicate with the sentence: "Previous research has suggested that non-inferiority margins should be half of the mean controlled effect size from historical trials."
3. From their meta-analysis they conclude that treatment is superior to controls by 0.7 SD units.
4. Convert this 0.7 SD units to an actual PHQ-9 value (= 3.8 PHQ-9 units).
5. Take half of this as suggested in step 2 - this is how they arrive at 1.9 PHQ-9 units.

So, if we follow this logic and apply it to our EPDS mean estimate of 7.93 (SD=4.68):

1. 0.7 SD units translates to 3.28.
2. Half of 3.28 is EPDS=1.64.

Applying this approach, our 13% margin of non-inferiority (which is 1.03) falls under this value.

2. Variables

A detailed list of variables can be found in [Appendix 1](#). Additionally, the Data Dictionary Codebook is available from the Data team.

3. Data analysis plan

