3.4. Outcome analysis

3.4.1. Primary Analysis

All analyses will be run as both intent-to-treat (ITT, i.e., group that the participant was randomized to) and per protocol (i.e., group participant actually participated in*). SAS Version 9.4³⁵ or later will be used for all analyses. For non-inferiority analyses, a successful result will be based on the upper bound of the 95% confidence interval being less than or equal to the non-inferiority margin. Based on recent guidelines^{28, 29}, we will not adjust our two primary hypotheses for multiplicity as they do not involve different endpoints (i.e. both hypotheses test EPDS scores). For secondary superiority hypotheses, a two-sided significance level of $p<0.05$ will be used to denote statistical significance. Descriptive statistics will be calculated for all variables of interest. Continuous measures such as age and depressive symptoms will be summarized using means and standard deviations, whereas categorical measures will be summarized using counts and percentages.

*Note: The trial has n=21 protocol deviations. This number has been consistent since the last major COVID wave (March 2022).

Demographic (e.g., ethnicity, age, marital status) and other baseline variables (e.g., severity and chronicity) will be compared for potential differences between study groups (TM vs IP, and SP vs NSP) using two sample two sided t-tests for continuous variables (or Wilcoxon rank sum test in the case of non-normal data), and chi-square analyses for categorical variables (Fisher's exact tests in the case of low expected cell sizes). Those who withdrew from the trial will be compared to those who continued on baseline indices including maternal education and occupation.

The primary outcome of non-inferiority in EPDS scores will be compared between NSP vs. SP and TM vs. IP groups at 3-months using a t-test with a 10% and 13% margins of non-inferiority, respectively.

Primary Aim 1: Examine if a brief, BA psychological treatment delivered by non-specialist providers (NSP) is as effective in treating perinatal depressive symptoms as specialist-delivered treatment.

Aim 1 is to show that NSP is non-inferior to SP (N=479 per group, SPs vs NSPs, [Table 3](#)).

Primary Aim 2: Examine if a brief BA psychological treatment delivered through telemedicine (TM) is as effective in treating perinatal depressive symptoms as in-person treatment (IP).

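### The telemedicine margin was widened from 10% to 13% for recruitment reasons, without explaining why 10% was dropped for mode alone, and the supporting sample-size figures do not fit the planned 958:268 comparison

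*SAP*

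**What the plan says.** SAP 1.6 attributes the revised sample-size approach to the pandemic. SAP 1.6.2.1 is specific: IP recruitment was difficult, and in response "the non-inferiority margin for the TM vs. IP comparison was increased from 10% to 13%, thereby reducing the required IP sample size". It then applies an effect-size argument (half of 0.7 SD, or 1.64 EPDS points, which exceeds 1.03) and mentions an EPDS trial with a 15% margin. Protocol 2.6 adds a 14% precedent.

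The two comparisons now have different margins on the same scale at the same visit. For provider: "Using a non-inferiority margin of 10% (i.e., EPDS score of 0.79 in relation to the mean". For mode: "Using a non-inferiority margin of 13% (i.e., EPDS score of 1.03 in relation to the mean". SAP 3.4.1 tests them "using a t-test with a 10% and 13% margins of non-inferiority, respectively". Success is defined by the "upper bound of the 95% confidence interval being less than or equal to the non-inferiority margin". The examples of sensitivity analyses in SAP Table 6 include no reading of TM vs IP at 10%.

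The size of the mode comparison is described in three ways:
- SAP Table 4 and the Aim 2 text in SAP 3.4.1 give 268 per group.
- SAP 1.6.2 asks for 268 additional IP women and continues: "When combined with the 958 TM participants, this yields a total study sample size of N=1,226". Table 5 gives this comparison 80% power.
- SAP 1.5 aims for equal IP and TM numbers in the final sample, and Protocol 2.8 for four equal arms.

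**The concern.** A non-inferiority margin states how much loss is acceptable. Here it moved during the trial, and the reason given is feasibility rather than a revised view of acceptable loss. The half-of-0.7-SD argument sets a ceiling that 0.793 also satisfies, so it cannot explain the move from one value to the other, or why only one comparison moved.

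The trade-off that justified the change is also presented through an equal-groups calculation, although the plan pairs 268 IP women with 958 TM women. A reader of Tables 4 and 5 cannot see what power the trial has at either margin.

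What is at stake is interpretation. An upper bound between 0.793 and 1.031 would be reported as non-inferior, although it fails the margin the trial started with. The plan specifies nothing that would bring this out.

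**Working it through.** **Inputs.** Mean 7.93 and SD 4.68 (SAP 1.6.2); margins 0.10 × 7.93 = 0.793 and 0.13 × 7.93 = 1.0309; true difference 0 (SAP Table 3, assumed to apply to mode as well); 10% dropout; target power 80%. The SAP states alpha 0.05 without a side. The success rule, read as a two-sided 95% interval, corresponds to one-sided 0.025, so both are shown.

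**1. The plan's own figures.** With equal groups, n = 2 (z₁₋α + z₀.₈₀)² SD² / margin². At one-sided 0.05 the numerator is 2 × (1.645 + 0.842)² × 4.68² ≈ 270.8.
- 10%: 270.8 / 0.793² = 431. Matches Table 3.
- 14%: 270.8 / 1.1102² = 220 (221 with the t distribution). Matches Table 4.
- 13%: 270.8 / 1.0309² = 255 (256 with the t distribution). Table 4 says 241.

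So the sizing used one-sided 0.05, and only the 13% row fails to reproduce. With 241 per group the power at 1.0309 is 78%. The figure 241 would fit a margin of 1.06, or 13.4%. The dropout step, 241 / 0.9 = 268, is right. With 256 it would be 285 per group.

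**2. The planned allocation.** After 10% loss, 958 and 268 become about 862 and 241. SE = 4.68 × √(1/862 + 1/241) = 0.341. Power ≈ Φ(margin/SE − z₁₋α); non-central t values are shown.

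| Evaluable TM vs IP | Margin | One-sided 0.05 | 95% CI rule |
|---|---|---|---|
| 862 vs 241 (SAP 1.6.2) | 13% | 92% | 86% |
| 862 vs 241 | 10% | 75% | 64% |
| 241 vs 241 (Table 4) | 13% | 78% | 67% |
| 241 vs 241 | 10% | 58% | 46% |
| 551 vs 551 (equal numbers, SAP 1.5) | 10% | 88% | 80% |

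The 80% in Table 5 matches neither 13% row. Table 5 does credit the provider comparison with the whole sample: its 88% is the 551 vs 551 value at one-sided 0.05. It makes no such adjustment for mode.

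**3. IP women needed for 80% power at 10%, using all 862 evaluable TM women.**
- One-sided 0.05: 288 evaluable; 288 / 0.9 = 320 randomised; 320 − 268 = 52 more.
- 95% CI rule: 402 evaluable; 402 / 0.9 = 447 randomised; 447 − 268 = 179 more.

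**4. What the wider margin changes.** Under the 95% CI rule with 862 vs 241, the largest observed TM minus IP difference that succeeds is 1.031 − 1.96 × 0.341 = 0.36 points at 13%, and 0.793 − 1.96 × 0.341 = 0.12 at 10%. If the true difference is 0, the chance of passing 13% but failing 10% is 85.6% − 64.2% ≈ 21%. At one-sided 0.05 it is 91.6% − 75.2% ≈ 16%.

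**The case against.** The plan has a fair defence. The change is disclosed with its reason. The new margin is 1.031 / 4.68 = 0.22 SD, below the plan's own 1.64 ceiling and below the 14% and 15% precedents it cites. Margins may differ between comparisons. Both appear in EPDS points, and any reader given the interval can compare it with 0.79. Using equal groups is conservative at 13% if all TM women are analysed. All of this stands, and it is why 13% can remain the primary criterion. It does not supply the missing reason for treating mode and provider differently.

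A reader might infer two stronger things.

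*That the margin was moved in the light of results.* Table 4 is labelled for Phase 3 and cites current 3-month dropout, so outcomes were accruing, and participants and providers are unblinded (Protocol 2.9). But no interim analysis is planned (Protocol 3.5.2, SAP 3.4.2.1), and data given to the principal investigator and biostatistician are to be blinded to allocation (Protocol 5.3). Monitoring-board reports include efficacy data (Protocol 4.2), but the board's members are not directly involved in the study (Protocol 4.1). The documents do not show that outcomes by arm played a part. They also do not state that the change was made without that knowledge.

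*That 10% was nearly affordable, so the need was overstated.* The figure of 52 more IP women needs both one-sided 0.05 and use of every TM woman. The SAP's interval rule raises it to 179. Many TM women were randomised while the IP arms were closed (SAP 1.5). If only 241 of them were usable, power at 10% would be 58% or 46%.

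**Conclusion.** The concern holds in two parts. First, the stated ground for widening the margin is recruitment, and the clinical argument shows only that 13% may be tolerable; it gives no reason for abandoning 10% for mode while keeping it for provider. Second, the supporting numbers are wrong for the comparison planned in SAP 1.6.2: power at 13% is 92% or 86% rather than 80%, power at 10% is 75% or 64%, and the 13% row of Table 4 is too small even on its own terms (241 against 256 per group).

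This does not mean that the trial is underpowered at 13%. With 862 vs 241 evaluable it exceeds the 80% target under either alpha. The cost of keeping 10% is best given as a range, 52 to 179 more randomised IP women, and higher if not all TM women can be used.

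These results assume SD 4.68, no true difference, 10% loss and the 958:268 allocation. SAP 1.5 and Protocol 2.8 describe a different allocation, so the figures stay conditional until that is settled. With 20% loss (766 vs 214), power at one-sided 0.05 would be 89% at 13% and 71% at 10%.

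**What to change.** - Reconcile Protocol 2.8 and SAP 1.5, 1.6.2 (Tables 4 and 5) and 3.4.1 on how many TM and IP women enter the mode comparison.
- Correct the 13% row of Table 4. At one-sided 0.05 it is 256 per group, or 285 per group (570 in total) with 10% dropout.
- In Table 5 and SAP 1.6.2.1, give the power of the actual TM:IP allocation at both margins, under the alpha that the decision rule implies.
- Keep 13% as the primary criterion. In SAP 3.4.1, pre-specify a supportive reading of the same TM minus IP interval against 0.793. If results by arm are already known when this is added, label it post hoc.
- In SAP 1.6.2.1, say why mode and provider have different margins, when the margin was changed, and, if true, that it was changed without knowledge of outcomes by arm.

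The cost is SAP and protocol wording and a few power calculations. No further recruitment or new model is needed, because one interval is read against two lines. The downside is that a result passing only at 13% will look less robust.

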3.1. Recruitment and Representativeness of Recruited Participants

Initial analyses will include examining the number of:

- patients that declined to consent and reasons,
- participants that consented, and
- eligible participants.

Analyses will also be conducted by intervention arm, examining the number of:

- participants allocated to each arm,
- participants that completed treatment and treatment compliance, and
- participants that completed the 3-, 6- and 12-months post-treatment assessments.

Recruitment data and representativeness of recruited participants are collected in the CONSORT flow chart. Participants are consented and randomized to one of the four arms at each of the 5 sites [Sinai Health, Women's College Hospital, St. Michael's Hospital (referral-site only), UNC, NorthShore] within the 3 Hubs (Toronto, Chicago, Chapel Hill). However, given the availability of treatment providers, patients may be referred to another site to enroll and randomize (in

Toronto, only). In this event, the collected data will be adjusted for site correlations due to potential site differences.

3.2. Withdrawals or Dropouts and Other Missing Data

The number and proportion of participants that are withdrawn from the trial or discontinue treatment will be reported overall and across arms at the following time points: screening, enrollment, treatment, and post-treatment at 3, 6 and 12 months. The reasons for withdrawal from the trial and discontinuing treatment will also be documented.

3.3. Adverse and Serious Adverse Event Reporting

Adverse events (AE) and serious adverse events (SAE) will be summarized (proportion of individuals with each type of AE/SAE, and total number of AEs/SAEs) by arm. Based on the final number of AEs/SAEs, the risks and 95% confidence intervals (CIs) may be reported, and the risks will be compared across intervention arms.

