#### 4.4. Safety Protocols

Safety protocols for both the recruitment research assistant and the treatment provider have been adapted from previous studies (detailed in *Appendix A –Safety Protocols and Forms*). In brief, a multistep process will be followed:

- Monitoring treatment quality. BA delivery will be extensively monitored during the study using previously established methods developed and tested by the PI.
  - ➤ Training Phase. During the training phase, clinical leads will host weekly supervision meetings with NSPs and specialist providers to review and discuss cases and reinforce BA training. Independent consultants will evaluate treatment among 5% of all audio sessions to assess treatment adherence and fidelity. Treatment providers not reaching the mean cut-off for specific items will receive refresher training by the study clinicians. In addition, quality indicators of NSP and specialist-delivered sessions will be collected including the number, mode of delivery and duration of sessions.
  - ➤ Trial Phase. During the trial phase, NSPs will continue to attend weekly supervision meetings to review and discuss cases. Once per month, clinical leads and NSPs will rate individual audio-recorded sessions for therapy quality—the extent to which a psychological treatment was implemented well enough to achieve its expected effects—of audio-recorded sessions in a monthly structured supervision. Audio recordings will be rated using the 20-item Q-HAP for BA-treatment-specific and common (e.g., collaboration, empathy) skills. The individual NSP who conducted the session (self-rating), two to three peers (peer ratings) and a clinical lead (expert rating) will rate each session. The summed score for each subscale will be used to estimate therapy quality for each NSP and compared to expert ratings. Specialists will not attend regular supervision, but supervision will be available to them on an ad hoc basis to reflect real-world conditions.
  - ➤ Independent consultants will continue to evaluate treatment among 5% of all audio sessions, by both NSPs and specialists, to assess treatment adherence and fidelity. Treatment providers not reaching the mean cut-off for specific items will receive refresher training by the study clinicians.

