Depressive Symptoms ⁸	Edinburgh Postnatal Depression Scale (EPDS) ^{8,9}	Mean continuous score of a 10-item scale (0-30). Severity ranges: none or minimal depression (0-9), mild (10-11), moderate (12-19), severe (>19)
Anxiety Symptoms	Generalized Anxiety Disorder Scale (GAD-7) ^{10,11}	Mean continuous score of a 7-item scale (0-21). Cut-off value (10)
Response & Remission	Patient Health Questionnaire-9 (PHQ-9) ¹²	Response: PHQ<10 Remission is defined as PHQ<5
Perceived Support	Multidimensional Scale of Perceived Social Support (MSPSS) ¹³	Mean continuous score of a 12-item scale (1-84)
Disability Assessment	World Health Organization Disability Assessment Schedule (WHODAS) ¹⁴	Mean continuous score of a 12-item scale (0 – 48)
Quality of Life Assessment	EQ5D-5 Level (EQ5D-5L) ¹⁵	Mean continuous score of a 5-item scale (1-25)
Trauma Symptoms	Abbreviated PTSD Checklist (PCL-6) ¹⁶⁻¹⁸	Mean continuous score of a 6-item scale (1-30). Cut-off value [14 (threshold) and 8 (subthreshold)]
Patient-Reported Activation	Premium Abbreviated Activation Scale ^{19, 20}	Mean continuous score of a 5-item scale (0-20)
Patient Satisfaction***	Client Satisfaction Questionnaire-8 (CSQ-8) ²¹	Mean continuous score of an 8-item scale (1-32)
Therapeutic Alliance***	Working Alliance Inventory-Short Revise (WAI-SR) ²²	Mean continuous score of a 12-item scale (1-60)
Health Service Utilization	Health Service Utilization Questionnaire (HSU-Q) ²³	Total score of a 16-item scale (0-32)
Treatment Preference**	Delivery of treatment and treatment provider preference	Score of 0 or 1
COVID-19 Exposure ⁹	1-item question on COVID-19 exposure	Self-reported
Health Benefits Access and Use	2-item question on access and use of health benefits	Self-reported
Treatment: Measured at every session during treatment, unless otherwise indicated		
Dosage	Treatment Log ²⁴	Number of Sessions Attended
Therapy Quality****	Quality of Healthy Activity Program (Q-HAP) ²⁵	Mean continuous score of treatment-specific BA skills (0-4) and general counselling skills (0-4)
Session Depressive / Anxiety	Session-by-session EPDS ⁸ and GAD-7 ¹⁰ scores	Mean continuous score of a 10-item scale (0-30) on EPDS and of a 7-item scale (0-21) on GAD-7
Homework Adherence	Treatment Log ²⁴	Mean continuous score of a 1-item question (0-2)
Adverse or Serious AEs	Anytime an Adverse Event (AE) or Serious AE (SAE) occurs	Any event that represents a serious threat to the safety of the mother or her child (see Appendix D of protocol)

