Appendix 1. List of Variables

VARIABLE	MEASURE	TIME OF ASSESSMENT						
		SCREENING	BASELINE	SESSION-WISE	3 MONTHS	6 MONTHS	12 MONTHS	HOME VISIT
PRIMARY OUTCOME								
Depressive symptoms	Edinburgh Postnatal Depression Scale (EPDS)							
SECONDARY OUTCOMES								
Depressive symptoms	Edinburgh Postnatal Depression Scale (EPDS)							
Anxiety Symptoms	General Anxiety Disorder-7 (GAD-7)							
Child Mental Development	Bayley-IV							
Psychosocial Stimulation	Home Observation Measurement Evaluation (HOME)							
EXPLORATORY OUTCOMES								
Response & Remission	Patient Health Questionnaire (PHQ-9)							
Suicide Risk*	Columbia Suicide Severity Risk Screener (C-SSRS)							
Patient-Reported Activation	Premium Abbreviated Activation Scale (PAAS)							
Quality of Life Assessment	EQ5D-5-level (EQ5D-5L)							

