Perinatal history: Breastfeeding	Plan for feeding infant							
Perinatal history: Breastfeeding	Pain, if any, breast feeding during the following time periods							

Notes: MC=Multiple Choice.

TREATMENT PROVIDER VARIABLES			
VARIABLE	MEASURE	TIME OF ASSESSMENT	
		ENROLLMENT	SUPERVISION SESSION-WISE
Provider characteristics: Age	Self-reported age (years)		
Provider characteristics: Sexual orientation and gender identity (MC)	Gender		
Provider characteristics: Sexual orientation and gender identity (MC)	Gender Identity		
Provider characteristics: Sexual orientation and gender identity (MC)	Sexual orientation		
Provider characteristics: Ethnicity (MC)	Ethnicity		
Provider characteristics:	Designation (NSP/SP)		
Provider experience	Experience implementing evidence-based psychological treatments prior to SUMMIT (Y/N)		
Provider experience	Experience seeing patients using telemedicine prior to SUMMIT (Y/N)		
Weekly Supervision	Provider Attendance		
Measurement-Based Supervision	Q-SUMMIT (Adapted from Quality of Healthy Activity Program: Q-HAP)		
Therapy Quality	Q-SUMMIT (Adapted from Quality of Healthy Activity Program: Q-HAP)		

Notes: MC=Multiple Choice.

Other forms collected, when applicable:

- *Columbia Suicide Severity Rating Scale – Cox and Holden completed at any time point if a participant:
 - Has a positive verbal response to self-harm
 - Scores >0 on question 10 of the EPDS
 - Scores >0 on question 9 of the PHQ-9
- Infant Harm By A Child

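### SAP 3.3 compares adverse event risks across arms without standardised ascertainment, and prespecifies no between-group analysis of the self-harm items collected from all women on one schedule

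*SAP*

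**What the plan says.** **Planned comparison.** SAP 3.3 says that "Adverse events (AE) and serious adverse events (SAE) will be summarized" by arm, as the proportion of women with each type of event and as total counts. It then says that "the risks and 95% confidence intervals (CIs) may be reported, and the risks will be compared across intervention arms", and makes the intervals depend on how many events occur. The section names no data source, observation window or method. It also names no analysis population, although SAP 3.4.1 says in general that analyses are run both as intent-to-treat and per protocol.

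**How events are recorded.** SAP Table 2 places AEs and SAEs in the block headed "Treatment: Measured at every session during treatment, unless otherwise indicated", but the row carries its own timing: "Anytime an Adverse Event (AE) or Serious AE (SAE) occurs". Protocol 3.4.1 says that the provider collects treatment data.

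**Supervision in the trial phase.** Under Protocol 4.4, NSPs go on meeting weekly to review cases. For the other group: "Specialists will not attend regular supervision, but supervision will be available to them on an ad hoc basis to reflect real-world conditions". A later bullet of the same section, on extensive training, describes weekly supervision with a clinical lead for all providers, specialists included.

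**Suicide risk.** SAP Appendix 1 lists it as an exploratory outcome measured by the C-SSRS, with only the screening box ticked. An asterisk leads to a note that the form is also completed at any time point on a trigger. One trigger is "Scores >0 on question 10 of the EPDS"; the others are PHQ-9 item 9 above zero and a positive verbal response on self-harm.

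**Items collected from everyone.** Appendix 1 schedules the EPDS and the PHQ-9 at 3, 6 and 12 months. Protocol 2.9 has these assessments completed through REDCap links in every arm.

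**The concern.** A between-arm comparison of event risks can be read at face value only if an event has the same chance of being recorded in each arm. Here events are reported as they come to light, and one provider group has a standing weekly occasion to discuss its cases while the other, on the trial-phase text, does not. A higher recorded risk under NSPs could then reflect closer review, and a similar recorded risk could hide a real difference. Provider type is the randomised factor of Primary Aim 1, and a conclusion that NSPs can deliver this treatment will be read alongside the harms table.

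The plan also passes over more comparable data. Screening C-SSRS precedes randomisation and so cannot compare arms. The self-harm items at follow-up can, because they come from the women themselves on one schedule, but no section of the SAP assigns them an analysis.

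**Working it through.** The documents give no AE risk, detection rate or safety sample size, so there is no stated figure to reproduce. The check has three parts.

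**1. Ascertainment, text against text**

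| Feature | NSP vs SP | TM vs IP |
|---|---|---|
| Trial-phase case review (Protocol 4.4) | Weekly vs ad hoc | No difference documented |
| Monthly research-team evaluation, including SAEs (Protocol 4.4) | Same | Same |
| Safety response to a positive self-harm item (Protocol 4.4) | Same | Same |
| EPDS and PHQ-9 at 3, 6, 12 months by REDCap link (Protocol 2.9, SAP Appendix 1) | Same | Same |

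The only documented asymmetry lies on the provider factor. The last row is common to all arms and does not pass through the provider.

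**2. What unequal detection would do (assumed rates)**

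Take the same true risk p in both groups, detection d1 and d2, and n = 1,226/2 = 613 per provider group (an even split is assumed).

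- Apparent risk ratio = (p × d1)/(p × d2) = d1/d2, whatever p is.
- Apparent risk difference = p × (d1 − d2).
- Chance of a spurious two-sided p<0.05 = Φ(z − 1.96) + Φ(−z − 1.96), where z is the risk difference divided by √[r1(1−r1)/n + r2(1−r2)/n] and r = p × d.

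| d1 vs d2 | Risk ratio | p = 2% | p = 5% | p = 10% |
|---|---|---|---|---|
| equal | 1.00 | nominal 5% | nominal 5% | nominal 5% |
| 90% vs 75% | 1.20 | 0.3 points, about 7% | 0.75 points, about 10% | 1.5 points, about 16% |
| 90% vs 60% | 1.50 | 0.6 points, about 14% | 1.5 points, about 28% | 3.0 points, about 51% |

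Each cell of the last two rows gives the apparent risk difference and the chance of a spurious result. Exchanging the groups reverses the sign.

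**3. Precision by choice of contrast**

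95% CI half-width = 1.96 × √[p(1−p)(1/n1 + 1/n2)], with p = 5% assumed. Group sizes come from SAP Table 5 (958 telemedicine, 268 in-person, 1,226 in total), with even splits by provider assumed.

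- Two in-person arms, 268/2 = 134 each: 1.96 × √(0.0475 × 2/134) = 5.2 points.
- Two telemedicine arms, 958/2 = 479 each: 1.96 × √(0.0475 × 2/479) = 2.8 points.
- NSP vs SP, 613 each: 1.96 × √(0.0475 × 2/613) = 2.4 points.
- TM vs IP, 958 vs 268: 1.96 × √[0.0475 × (1/958 + 1/268)] = 3.0 points.
- TM vs IP with the 268 per group named in SAP 3.4.1: 1.96 × √(0.0475 × 2/268) = 3.7 points.

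The last two lines differ because many telemedicine women were randomised while no in-person arm was open (SAP 1.5). An analysis that respects randomisation phase cannot use them all for this contrast.

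Loss to follow-up widens the self-harm comparisons a little. With 10% lost, 613 × 0.9 ≈ 552 per provider group, and 1.96 × √(0.0475 × 2/552) = 2.6 points.

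**The case against.** The strongest reply is that harm surveillance is broader than SAP 3.3 suggests. A reader might infer that the safety comparison rests wholly on what providers notice in sessions. The documents do not support that. The AE row of SAP Table 2 is not tied to sessions. Protocol 4.4 adds a monthly research-team evaluation that includes SAEs, study-team review of worsening session scores, and a follow-up protocol for self-harm and infant harm. SAP Table 6 plans a sensitivity analysis on women with an SAE after randomisation but before treatment, so events are captured in women who had not begun treatment. The protocol's appendices on safety and adverse events are also not among the documents reviewed. All this stands and reduces the concern. It does not show that every woman is asked the same question at the same times.

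A reader might also infer that suicide risk is not assessed after screening. The Appendix 1 note says otherwise, and at follow-up the item triggers are the same in every arm. The triggered form is a useful second stage, but its first stage, the item response, has no planned analysis. Nor does the trial lack like-for-like harm data: it holds them and prespecifies no use of them.

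On supervision, the extensive-training bullet conflicts with the trial-phase text. It can be read as describing the training period, but it does not say so. If specialists do have weekly supervision, the documented asymmetry goes. The case for analysing the self-harm items remains.

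Finally, safety is not a stated objective, and making intervals depend on event counts is defensible for very rare events. That limits the weight of the point.

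**Conclusion.** The concern holds in a limited form. Detection of AEs and SAEs may differ between NSP and SP because trial-phase case review differs, and the other surveillance routes lessen this without standardising it. The documents show neither the size nor the direction of any bias. The apparent risk ratios of 1.20 and 1.50 rest on assumed detection rates and show only that moderate inequality would matter. Nothing in the documents supports extending the supervision argument to TM versus IP.

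Two points do not depend on assumed detection rates. First, suicide risk is a named exploratory outcome with no scheduled C-SSRS after randomisation, and the self-harm items due from all women have no between-group analysis. Second, a comparison across four arms is less precise than one on the randomised factors: at an assumed 5% risk, about 5.2 points between the in-person arms against 2.4 for NSP versus SP. This should be changed, but it does not threaten the primary analysis.

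**What to change.** - **Add outcomes.** In SAP 3.3 and Appendix 1, add EPDS item 10 above zero and PHQ-9 item 9 above zero at 3, 6 and 12 months as exploratory safety outcomes, with triggered C-SSRS results as supporting data.
- **Fix the contrasts.** Report risk differences with 95% CIs for NSP vs SP and TM vs IP. For TM vs IP, take account of randomisation phase, for example by stratifying on it. Report missing follow-up by group.
- **AE/SAE tables.** Present AE/SAE risks on the same two contrasts as well as by four arms. State the source, window, population and method, including whether events before treatment count. Note that ascertainment may differ by provider type.
- **Avoid one tempting endpoint.** Do not use any inpatient stay from the health service questionnaire unless birth admissions can be separated. SAP 3.4.2.4 expects up to 75% of the sample to receive antenatal treatment, so deliveries could dominate it.
- **Reconcile.** The two statements on specialist supervision in Protocol 4.4 must be reconciled.

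The cost is SAP wording and a few tables from data already collected. The downside is that the items are self-reported screening responses, not adjudicated events, and are subject to loss to follow-up (10% in the sample size; 20% expected in Protocol 3.2).
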